6.1.1 Full Analysis Dataset (FAS)

All participants randomised into the study. Participants will be analysed according to treatment to which they were randomised. Immunogenicity analyses performed in the FAS are considered supportive.

6.1.2 Safety Analysis Dataset (SAF)

All randomised participants who received at least one dose of IP. Participants will be analysed according to the treatment received.

6.1.3 Intention-to-Treat (ITT) Analysis Dataset

All randomised participants who received at least one dose of IP and have an evaluable baseline and post-baseline blood sample (at least one post baseline dose of RV3-BB). Participants will be analysed according to the treatment to which they were randomised. All analyses performed using the ITT set will be considered supportive.

6.1.4 Per-protocol (PP) Analysis Dataset

All participants from the ITT population who completed the study in compliance with the protocol and who reported no major violation of the study protocol which may have effect on the primary endpoint. Participants will be analysed according to the treatment to which they were randomised. Primary analyses will be performed on the PP set.

7. General considerations

7.1.1 Visit and date conventions

Visit day will be calculated from the reference treatment start date which will be used to present start/stop day of assessments and events. The reference treatment start date is defined as the date of first IP administration. The following conventions will be used for visit references:

- Visit day = date of event reference treatment start date
- Visit week = $\frac{visit \, day}{7}$, rounding up to next whole number

No visit windowing (i.e. remapping of visits based on visit windows) will be performed for this trial. The assigned nominal visit will be used for by-visit summaries. In the situation where the assessment/event date is partial or missing, visit day/week/month, and any corresponding durations will appear missing in the data listings. Unscheduled measurements will not be included in by-visit summaries. Trial visit will be assigned as below (see section 4.3, Schedule of Events):

Pre-study: Second trimester to birth

Preliminary consent, cord blood collection and maternal blood sampling will happen during this period.

Visit 1 (Day 1; birth to 144 hours old)

Participants will return to the trial site for Day 1 procedures and maternal blood samples will be collected.

Visit 2 (Day 8; 7±1 days post visit 1), Visit 4 (Week 7; 7±1 days post visit 3), Visit 6 (Week 11; 7±1 days post visit 5), Visit 8 (Week 15; 7±1 days post visit 7)

Participants will return to the trial site for vital sign measurements, feeding review, AE and concomitant medication recording.

Visit 3 (Week 6; + 7 days), Visit 5 (Week 10; \pm 7 days and at least 21 days post visit 3), Visit 7 (Week 14; \pm 7 days and at least 21 days post visit 5), Visit 9 (Week 18; \pm 7 days and at least 21 days post visit 7)

Participants will return to the trial site for Week 6/10/14/18 procedures.

7.1.2 Baseline

Unless otherwise specified, Baseline is defined as the last non-missing observation taken prior to IP administration.

Due to the timing of the blood tests, baselines for serum anti-rotavirus IgA are defined differently for participants in the neonatal vaccine schedule and the infant vaccine schedule. Baseline serum anti-rotavirus IgA in the neonatal vaccine schedule is defined as the measurement from the cord blood. In the infant vaccine schedule baseline is defined as the measurement from analysis of serum collected prior to the second dose, although the measurement from the cord blood/visit 1 venous blood may be used if there are no data on IgA following the first dose of IP. Note that where cord blood is unavailable for collection, a venous blood sample can be collected at Visit 1 prior to IP administration. See section 8.1.3 for details.

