3.8.1 Phase I clinical study of RV3-BB

This single-centre, double-blind, randomised placebo-controlled study evaluated the safety and tolerability of a single 1mL oral dose of RV3-BB in a total of 60 participants across three age groups (Protocol MCRI-RV3-BB-001). The study was completed in 2011 in Melbourne, Australia.

A single dose of vaccine or placebo was administered initially to 20 adult males aged 18-50 years (Cohort 1), progressing to 20 children aged 3-8 years (Cohort 2), then to 20 infants aged 6-8 weeks (Cohort 3). Each cohort included 10 vaccine and 10 placebo recipients. The results demonstrate that the single dose of vaccine was well tolerated in adults, children and infants (Danchin et al., 2013). Evaluation of vital signs revealed no clinically significant changes in any participant. There were no clinically significant abnormalities in haematology. Clinically significant increases in serum ALT above the upper limit of normal (ULN) were reported at the Day 28 time point for 5 participants in cohort 3 (4/10 vaccine, 1/10 placebo). All ALT abnormalities had resolved on follow up with no evidence of long-term consequences. No AEs were considered to have a definite or probable relationship to the study vaccine. One SAE was reported in Cohort 3; this was an episode of pneumonia in the vaccine group that was assessed by an independent physician as unrelated to the IP.

Vaccine response was a secondary objective in this trial, although it was expected that there would be limited immune response following a single dose of vaccine. In Cohort 3 a serum immune response (>3-fold increase in SNA and/or IgA from baseline) was identified in 5/9 infants receiving RV3-BB (56%) compared to 2/7 placebo recipients (28%). A vaccine response, defined as evidence of RV3-BB -BB rotavirus replication detected in stool between day 3-6 and/or response of serum IgA or SNA, was observed in cohort 3 in 8/9 infants receiving RV3-BB (89%) and 2/7 placebo recipients (28%). The data from the Phase I trial of RV3-BB are promising in that excretion consistent with viral replication occurred in the majority of infants after a single dose of RV3-BB.

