4.2 Secondary Objectives

The secondary objectives of the study are;

- To assess the cumulative anti-rotavirus serum IgA response (defined as a ≥3 fold increase from baseline) 4 weeks after 3 doses of RV3-BB administered in an infant schedule at a vaccine titre of 1 x 10⁷.
- To assess cumulative vaccine take and components of vaccine take after 3 doses of RV3-BB (titre of 1 x 10⁷) administered in a neonatal schedule versus three doses of RV3-BB in an infant schedule at a vaccine titre of 1 x 10⁷.
- To assess cumulative vaccine take and the components of RV3-BB vaccine take after 3 doses of RV3-BB administered as a neonatal schedule at a vaccine titre of 1 x 10⁷, 3 x 10⁶ or 1 x 10⁶.

To assess cumulative vaccine take and the components of vaccine take after 2 doses of RV3-BB administered as a neonatal schedule at a vaccine titre of 1×10^7 , 3×10^6 or 1×10^6 or 2 doses in the infant schedule at a vaccine titre of 1×10^7 .

- To assess cumulative vaccine take and components of vaccine take after the first dose of RV3-BB administered as a neonatal schedule at a vaccine titre of 1 x 10⁷, 3 x 10⁶ or 1 x 10⁶ compared to placebo (1st dose of IP in the infant schedule).
- To assess cumulative vaccine take and components of vaccine take after the first dose of RV3-BB at a vaccine titre of 1 x 10⁷, 3 x 10⁶ or 1 x 10⁶ in the neonatal schedule compared with the first dose of RV3-BB at a vaccine titre of 1 x 10⁷ in the infant schedule.
- To describe the geometric mean titre of the anti-rotavirus serum IgA response after 3 doses of RV3-BB administered as a neonatal or an infant schedule
- To describe the safety and tolerability of RV3-BB when administered as an infant or as a neonatal schedule.
- To describe the occurrence of diarrhea episodes in participants, according to severity and detection of wild-type rotavirus.

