8.1.3 Missing data

Where possible, data from participants who withdraw prematurely from the study will be included in any analysis.

Participants with missing baseline IgA measurements will be assigned a value below the lower limit of detection (i.e assigned a value of 10) in the calculation of serum immune response (although the cord blood IgA value will still be acknowledged as missing when summarising titre). Partial date imputation of adverse events and concomitant medications are mentioned in respective sections.

9. Primary and Secondary Analyses

In order to be included in the analysis of cumulative vaccine take, participants must have at least one of IgA response or shedding data following any dose of IP

Where:

- 1. An IgA response is defined as a 3-fold rise from baseline, where baseline is defined as cord blood for neonatal comparison and post dose 1 blood for infant comparison (or cord if post dose 1 data is missing). It will be assumed that cord blood is 10 if cord blood is missing).
- 2. Shedding data is defined as having stool data for at least 1 time point from days 3-5 post vaccine.

All available data on IgA response, shedding at all time points (post dose 1, 2 and 3 for the neonatal comparison and post doses 2, 3 and 4 for the infant comparison) will be used to determine whether vaccine take is positive or negative for each individual, with participants classified as having a positive vaccine take if any response (IgA, or shedding days 3-5) at any time point is positive, and classified as negative for vaccine take otherwise (i.e. if all known measurements at all time points are negative).

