9.1.5 Cumulative Vaccine Take After Three Doses of RV3-BB

Baseline values of IgA measurement for the neonatal schedule will be obtained from analysis of cord blood. Baseline values of IgA measurements for the infant schedule will be obtained from analysis of sera collected prior to the second dose of investigational product.

Neonatal comparison - a positive cumulative vaccine take corresponds to a serum immune response post investigational product doses 1, 2 or 3 or detectable RV3-BB virus shedding in stool (days 3, 4 or 5) post investigational product doses 1, 2 or 3.

Infant comparison - a positive cumulative vaccine take corresponds to a serum immune response post investigational product doses 2, 3 or 4 or detectable RV3-BB virus shedding in stool (days 3, 4 or 5)) post investigational product doses 2, 3 or 4.

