9.1.7 Cumulative Vaccine Take After one RV3-BB Doses

The number and proportion of participants with cumulative vaccine take after the first RV3-BB dose (i.e., neonatal schedule with positive serum immune response post investigational product dose 1 or RV3-BB virus shedding in stool post investigational product dose 1 compared to "placebo" infant schedule with positive serum immune response post investigational product dose 1 or RV3-BB virus shedding in stool post investigational product dose 1 or RV3-BB virus shedding in stool post investigational product dose 1 or RV3-BB virus shedding in stool post investigational product dose 1 or RV3-BB virus shedding in stool post investigational product dose 1 or RV3-BB virus shedding in stool post investigational product dose 1 will be summarised, by treatment group for the neonatal schedule group and the "placebo" infant group, using frequency tabulations.

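### In the dose-1 comparison with placebo, the infant arm's IgA baseline is also its only post-dose-1 sample, so its IgA response is 0% by definition

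*SAP*

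**What the plan says.** **Baseline by schedule.** SAP 7.1.2 gives the neonatal arms a cord baseline: "Baseline serum anti-rotavirus IgA in the neonatal vaccine schedule is defined as the measurement from the cord blood". For the infant arm it says: "In the infant vaccine schedule baseline is defined as the measurement from analysis of serum collected prior to the second dose". Protocol 13.3.2.1 has the same rule, and SAP 9.1.5 repeats it for vaccine take: "Baseline values of IgA measurements for the infant schedule will be obtained from analysis of sera collected prior to the second dose". There is one fallback for the infant arm: "the measurement from the cord blood/visit 1 venous blood may be used if there are no data on IgA following the first dose of IP".

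**Baseline by comparison.** The opening text of SAP section 9 puts it differently: "baseline is defined as cord blood for neonatal comparison and post dose 1 blood for infant comparison".

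**The dose-1 contrast.** One secondary objective in protocol 4.2 assesses take and its components after the first neonatal dose "compared to placebo (1st dose of IP in the infant schedule". SAP 9.1.7 implements it by counting, in the placebo group, "infant schedule with positive serum immune response post investigational product dose 1 or RV3-BB virus shedding in stool". It names no baseline of its own.

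**Sampling.** Blood is taken as cord (or Visit 1 venous) blood, then before IP doses 2, 3 and 4, and at week 18 (protocol 5.1 and Table 1; SAP 4.1.1). An IgA response is a rise of at least 3-fold over baseline (SAP 3.1.1).

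**The concern.** The week-6 serum has two roles in the infant arm. It is the baseline for that arm's later vaccine doses, which is sensible. It is also the only sample that can show what happened after the placebo given as IP dose 1. If the schedule-based baseline is carried into 9.1.7, the placebo group's IgA result is settled by the definition before any data are seen, while the neonatal arms are measured from cord and can respond.

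From IP dose 2 onward every arm has received RV3-BB, so dose 1 is the only point at which vaccine can be compared with concurrent placebo in infants not yet given RV3-BB. Natural exposure by week 6 would count as response in the neonatal arms and could not count in the placebo arm.

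There is a smaller gap in the same section. Protocol 4.2 and SAP 2.1.2 also ask for the neonates' first RV3-BB dose against the infants' first RV3-BB dose, which is IP dose 2. SAP 9.1.7 covers only the placebo contrast.

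**Working it through.** The documents state no expected rate, power or sample size for this contrast, so there is no figure to reproduce. The check traces the definitions through the sampling schedule and then sizes the effect under stated assumptions.

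**1. Which sample is the post-dose-1 sample?** The draws are cord/Visit 1, Visit 3 (before IP dose 2), Visit 5, Visit 7 and Visit 9. Only Visit 3 falls after IP dose 1 and before IP dose 2.

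**2. Fold rise after IP dose 1.**
- Neonatal arms: Visit 3 IgA / cord IgA.
- Infant (placebo) arm, baseline by schedule: Visit 3 IgA / Visit 3 IgA = 1, which is below 3 for every infant.

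Example: a cord value below detection is set to 10 (SAP 9.1.3). A Visit 3 value of 30 then gives 30/10 = 3, a responder, in a neonatal arm. The same two values in the infant arm give 30/30 = 1, a non-responder.

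**3. Does the fallback help?** No. Cord replaces the infant baseline only when there is no IgA after dose 1. The post-dose-1 outcome is then missing too.

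**4. Effect on the IgA difference.** Let v be the neonatal-arm response rate and b the true background response at week 6, both measured from cord.
- Like-for-like difference: v − b.
- Difference as written: v − 0 = v.
- Overstatement: v − (v − b) = b.

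The documents give no value for b, so the values below are assumptions. A simulation of 100,000 infants per value confirmed the algebra.

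| Assumed b | Placebo response as written | Placebo response, cord baseline (simulated) | Overstatement (points) |
|---|---|---|---|
| 2% | 0% | 2.0% | 2 |
| 5% | 0% | 5.0% | 5 |
| 10% | 0% | 10.1% | 10 |
| 20% | 0% | 19.8% | 20 |

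**5. Effect on vaccine take.** Take is IgA response or shedding. Let s be the placebo shedding rate and j the rate of both.
- True placebo take: b + s − j.
- As written: s.
- Overstatement of the difference: b − j, which is at most b. Only placebo IgA responders who do not also shed are lost.

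**6. What an interval would show, if one were computed.** SAP 7.1.4 says immunogenicity and take are analysed inferentially as for the primary, but the Newcombe-Wilson interval in 9.1.2 is specified after dose 3. Suppose it were carried over to dose 1, with 172 × 0.7 ≈ 120 per arm in the per-protocol set. Against 0/120, five responders in a vaccine arm put the lower limit above zero. With no vaccine effect at all, the exact binomial probability of reaching five is 9% at b = 2%, 72% at b = 5% and 99% at b = 10%. These figures depend on both the assumed b and the assumed method.

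**The case against.** **The SAP can be read the other way.** Section 9 assigns cord to the 'neonatal comparison' and lists post-dose-1 outcomes only there. Section 5 speaks of comparisons that involve the neonatal schedule and use cord as baseline, and the dose-1 contrast does involve that schedule. Section 9.1.1 derives an infant-arm responder only for IP doses 2 to 4. On this reading cord would apply in both arms, or the rule is simply unspecified. The reading is possible, but the SAP never states it for this contrast. Sections 9.1.5 and 16.1.2 use 'neonatal comparison' and 'infant comparison' for each schedule's own doses, and 7.1.2, 9.1.5 and protocol 13.3.2.1 fix baseline by schedule. A programmer following those sections would produce 0%. Either reading needs the clarifying sentence.

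**Other dose-1 contrasts survive.** A reader might infer that the trial loses its only internal check against placebo. It does not. Vaccine-like shedding by dose and arm (9.1.8), and IgA geometric means and the proportion below detection at each time point (9.1.3), do not use this baseline. Week-6 background in the placebo arm would be visible in the titre tables. This part of the objection stands.

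**Section 9.1.7 asks only for frequency tables.** The general inferential sentence in 7.1.4 may extend to them, but the methods in 9.1.2 address lower titres against the high titre. This also stands, and is why step 6 is conditional.

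**The first-RV3-BB-dose gap is partial.** IgA response at each time point (9.1.4) and shedding by dose (9.1.8) already give the components after the infants' IP dose 2. Only the composite is missing.

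**Conclusion.** The point holds for one secondary objective. Under the schedule-based baseline the placebo arm's IgA response after IP dose 1 is 0% whatever the data. The IgA difference is overstated by the true week-6 background, and the take difference by at most that amount. The primary endpoint uses neonatal arms only and is untouched, and the week-6 baseline remains reasonable for the infant arm's responses to IP doses 2 to 4. This should be fixed before analysis, but it does not threaten the main conclusion.

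The size is unknown, and 2 to 20 points is an assumed range. A reader might be tempted to take it from figures in the protocol, but none of them measures a 3-fold IgA rise by week 6:
- The Phase I placebo result of 2/7 (section 3.8.1) counts SNA and/or IgA, in Melbourne infants dosed at 6–8 weeks. Its exact 95% interval is about 4% to 71%.
- The 42% in the Phase IIb neonatal placebo schedule (section 3.8.3) is cumulative take over the full course, in Indonesia, and includes shedding.
- The 40.4% in Malawian placebo infants (section 3.6.1) is seropositivity one month after the last dose. Spread evenly over an assumed 20 weeks it gives 40.4 × 6/20 = 12.1% by week 6; a constant hazard gives 14.4%. Both convert a different measure by assumption.

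Together these suggest that background is unlikely to be zero. They do not support a numerical range.

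Nor do the documents support saying that take is inflated by the whole placebo IgA rate; that is the upper bound.

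**What to change.** In SAP 7.1.2, the opening of section 9, and 9.1.7, state that for the post-dose-1 comparison of vaccine with placebo the IgA baseline is cord (or Visit 1 venous) blood in all four arms. Apply the same missing-baseline rule (8.1.3) and the same rule for cord values above 30 (section 5) in every arm. Keep the week-6 baseline in the infant arm for responses after IP doses 2 to 4.

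Add to 9.1.7 the infant arm's composite take after IP dose 2, as the comparator for the first-RV3-BB-dose objective.

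The cost is a sentence in each place, one derivation flag and one extra table column. Cord or Visit 1 blood is already planned in every arm, so no new sample or visit is needed.

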7.1.3 Stratifications

For analysis purposes, participants may be sub-classified into the following stratification levels, where applicable:

- Gender
 - o Male
 - \circ Female
- Delivery route
 - o NVD
 - Caesarean Section
- Race/predominant ethnicity
 - o American Indian or Alaska Native
 - o Asian
 - Black or African American
 - Native Hawaiian or Other Pacific Islander
 - o White
 - o Other
 - o **Unknown**
 - Not reported

7.1.4 Statistical tests

A single analysis will be performed at the end of the trial. No interim analyses are planned.

Primary Analysis:

The primary analysis and primary sensitivity analysis are based on the per protocol population defined as participants who receive all 3 doses of RV3-BB and have no major protocol violations (after reviewed and agreed at the end of the study). Thirty percent of participants are expected to be excluded from the PP population due to death, study withdrawal, loss to follow-up, or study non-compliance.

Non-inferiority of the lower titre vaccine will also be assessed in the intention to treat population. The cumulative probability of response by 18 weeks of age will be estimated by the Kaplan-Meier method for each vaccine arm. The difference between high and low titre arms in the cumulative probabilities and its 95% confidence interval will be calculated. If the upper bound of the confidence interval is below 20%, non-inferiority of the lower titre vaccine will be demonstrated.

Additionally, we will calculate the 95% CI of the binomial proportions using the method of Newcombe-Wilson without continuity correction and generalized estimating equations (GEE) after dose 3 on the PP and ITT analyses set.

All the primary and primary sensitivity analysis will be based on PP and ITT analysis set.

See section 10 for additional details.

Secondary Analyses:

Immunogenicity and vaccine-take results will be (inferentially) analysed as done for the primary analysis. Descriptive analyses are described in section 10.

Safety

No formal statistical testing will be performed on the safety data.

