6.11 Visit 9 (Week 18 ±7 days)

The following will be performed/recorded at the trial site, no sooner than 21 days after the previous dose of IP (Visit 7):

- Review AEs.
- Review concomitant medication.
- Review feeding status.
- Review Diarrhoea Log.
- Collect a pre dose blood sample.
- Vital signs (see section 8.3) within the 60 minutes pre dose.
- Administer Rotarix®.
- Administer any scheduled EPI vaccines according to local guidelines (see section 9.2).

Study staff will contact the parents/guardians (clinic or home visit) the day following dosing.

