10.5 Doses and treatment regimens

Approximately 688 participants will be prospectively randomised to one of the following four treatment groups in a 1:1:1:1 ratio.

- High dose neonatal RV3-BB vaccine schedule (1x10⁷titre dose). RV3-BB Vaccine for doses 1, 2 and 3 and placebo for dose 4
- Mid dose neonatal RV3-BB vaccine schedule (3x10⁶titre dose). RV3-BB Vaccine for doses 1, 2 and 3 and placebo for dose 4.
- Low dose neonatal RV3-BB vaccine schedule (1x10⁶titre dose). RV3-BB Vaccine for doses 1, 2 and 3 and placebo for dose 4.
- High dose Infant RV3-BB vaccine schedule (1x10⁷titre dose). Placebo for dose 1 and RV3-BB Vaccine for doses 2, 3 and 4

Participants will also receive a dose of commercially available Rotarix® at 18 weeks of age.

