1.1.1 Introduction

This document describes the rules and conventions to be used in the presentation and analysis of a phase II randomised, double blind, parallel group dose-ranging study of oral RV3-BB Rotavirus Vaccine administered at a titre of 1×10^7 , 3×10^6 or 1×10^6 as a 3 dose neonate schedule or administered at a titre of 1×10^7 as a 3 dose infant schedule.

This statistical analysis plan (SAP), is based on protocol MCRI-RV3-BB-004, version 04, dated 11-Jan-2019 and CRF, Version 05, Dated 22-Jul-2019.

2. Trial objectives

The following objectives are those stated in the protocol.

2.1.1 *Primary objectives*

The primary objective of this study is to assess a cumulative anti-rotavirus serum IgA response (defined as a \geq 3-fold increase from baseline) 4 weeks after 3 doses of RV3-BB administered in a neonatal schedule at a vaccine titre of 1x10⁷, 3x10⁶ or 1x10⁶.

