9.1.1 Variables and derivations

Primary endpoint:

A serum IgA response in the *neonatal* schedule, is defined as $a \ge 3$ -fold increase from baseline, where baseline is defined as stated in sections 7.1.2 and 8.1.3 for handling of missing baseline IgA measurements of this analysis plan.

Secondary endpoints:

- A serum IgA response in the *infant* schedule, is defined as a ≥ 3-fold increase from baseline, where baseline is defined as stated in sections 7.1.2 and 8.1.3 for handling of missing baseline IgA measurements of this analysis plan.
- Cumulative vaccine take is defined as vaccine take observed at the current assessment time point or following any previous dose, where vaccine take is

defined as \geq 3-fold increase in serum anti-rotavirus IgA from baseline to post IP dosing, or detectable RV3 shedding in stools (by ELISA or PCR) any day from day 3 to 5 following administration of IP.

- Shedding of RV3-BB is defined as presence of RV3-BB shedding in stool from days 3-5 following each dose of IP.
- Geometric mean titre of the anti-rotavirus serum IgA response after 3 doses of RV3-BB.
- Safety and tolerability (as per sections 15 to 16 of this analysis plan) of RV3-BB.
- Occurrence of diarrhoea episodes in participants, according to severity and detection of wild-type rotavirus.

Derivations:

A participant will, at each vaccine titre, be defined a "responder" if he/she has a serum *IgA response* (\geq 3-fold increase in serum anti-rotavirus IgA from baseline) for neonatal arms IP dose 1 - 3 and infant arm IP dose 2 - 4 of RV3-BB. The response rate will be dichotomised (0 = non-responder, 1 = responder).

Geometric means (and associated summary statistics) will be determined as follows:

- 1. Log-transform the titre data (if not already log-transformed)
- 2. Determine the arithmetic mean and other descriptive statistics of the transformed data using the PROC MEANS procedure
- Exponentiate the output obtained from the PROC MEANS procedure, depending on data to be presented (log-transfer vs not log-transformed)
- 9.1.2 Analysis

Non-inferiority of lower titre vaccines (primary as well as secondary endpoints):

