The difference between high and low titre arms in the response rate and its 95% confidence interval will be calculated. The cumulative probability of anti-rotavirus serum IgA response (as defined above) by 18 weeks of age will be estimated by the Kaplan-Meier method for each vaccine arm. PROC LIFETEST (SAS[®] Version 9.4 or above) will

be used to analyse the response rates (non-responder *vs.* responder). With the CENSOR variable, 1 is commonly used to indicate that an event occurred (subject is a responder) and 0 indicates that the event did not occur (the subject was censored/is a non-responder).

Non-inferiority of the lower titre vaccine will be demonstrated if the upper bound of the confidence interval is below 20%.

Additionally, we will calculate the 95% CI of the difference between vaccine groups in the serum IgA response rate after dose 3 using the method of Newcombe-Wilson without continuity correction for the difference between binomial proportions as implemented in PROC FREQ (SAS® Version 9.4 or above).

Generalized estimating equations (GEE) will be used to analyse the response rates (non-responder vs. responder) after dose 3 using PROC GEE (SAS® Version 9.4 or above). We will calculate a binary outcome ($1 = \ge 3$ -fold increase, 0 = < 3-fold increase from baseline) after dose 1, 2, and 3 for each participant who received vaccine according to the neonatal schedule. After that, we will fit a model with dose as a discrete/categorical/factor variable, vaccine group (low, medium, high dose) as a discrete variable, and dose by vaccine group interaction term. The model will use the binomial distribution for the outcome variable and the exchangeable correlation matrix to account for the correlation between a participant who received vaccine according to the neonatal schedule outcomes. Model will be used for the analysis. Once the model is fit, contrast statements will be used in PROC GENMOD (SAS® Version 9.4 or above) to calculate the difference in the response rate after dose 3 for the high versus low dose and so forth.

In the table, (Estimate, standard error, 95% CI) will be presented.

The general linear model to be fit by GEE is

 $logit(p_{ij}) = \beta_{ij}$

where p_{ij} is the response rate after the i-th dose in the j-th vaccine group. Differences between the β s represent the log odds ratio in response rates.

MCRI-RV3-BB-004

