20.1.16 Presentation of visits

- IP Dose 1 Visit 1 (Day 1)
- Post IP Dose 1 Visit 2 (Day 8)
- IP Dose 2 Visit 3 (Week 6)
- Post IP Dose 2 Visit 4 (Week 7)
- IP Dose 3 Visit 5 (Week 10)
- Post IP Dose 3 Visit 6 (Week 11)
- IP Dose 4 Visit 7 (Week 14)
- Post IP Dose 4 Visit 8 (Week 15)
- Post IP Dose 4 Visit 9 (Week 18)

21. Revision history

Version	Date	Change
1.0	16-Mar-2020	Initial version
2.0	28-May-2020	 "Not done" abbreviation added as "ND"
		 Exploratory endpoint updated in section 3.1.3
		• ITT and PP definition updated in section 6.1.3 and
		6.1.4 respectively
		 All the primary, primary sensitivity and secondary efficacy analysis population updated in section 9.1.2 and also updated All the primary, primary sensitivity analysis population in section 7.1.4
		 "Cohort" word replaced by "Treatment Group" in respective section.
		 Serum IgA listings added for Neonatal and infant as well as for mother in section 9.1.3 and 9.1.12 respectively.
		 Definition of a positive cumulative vaccine take are updated in section 9.1.5 and 9.1.6.
		 Diarrhea Table and listing variable updated in section 9.1.10
		 Protocol violations/deviations listing population updated in section 10.1.2
		 Demographic table and listing population updated, and Population information added for the Logistic regression model table in section 11.1.2
		 Exposure to IP table and listing population updated in section 12.1.2
		 IP administration data as well as compliance table and listing population updated in section 13.1.2
		 Medical history listing population added in section 14.1.2
		 Previous- and concomitant medications listing sorting order added in section 15.1.2.
		 Treatment emergent adverse events (TEAEs) word deleted from the SAP.
		 Adverse events listing population added in section 16.1.2
		 blood in stool listing population added in section 16.1.10
		• Vital sign parameter name added , Listing population

 added and deleted "change from pre- and post-vaccination assessment" line. New section 19 added for the feeding assessment Section 20 updated based on mock shells requirement
as appropriate.

22. Reference

- Biometrics, Vol. 57, No. 1. (Mar., 2001), pp. 120-125
- dx.doi.org/10.1016/j.vaccine.2014.08.011

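### The Kaplan-Meier non-inferiority rule runs to 18 weeks of age, which in the neonatal arms reaches past the endpoint sample (Visit 7) to the blood drawn after placebo dose 4

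*SAP*

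**What the plan says.** The primary objective (SAP 2.1.1, Protocol 4.1) is IgA response "4 weeks after 3 doses of RV3-BB administered in a neonatal schedule". The endpoint lists in Protocol 7 and SAP 3.1.1 also stop at 4 weeks after the third RV3-BB dose.

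Protocol 10.5 gives the neonatal arms "RV3-BB Vaccine for doses 1, 2 and 3 and placebo for dose 4" and the infant arm "Placebo for dose 1 and RV3-BB Vaccine for doses 2, 3 and 4". SAP 9.1.1 defines a responder accordingly, "for neonatal arms IP dose 1 - 3 and infant arm IP dose 2 - 4 of RV3-BB".

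The Kaplan-Meier rule uses one horizon for every arm. SAP 7.1.4, in the same words as the Protocol synopsis and Protocol 13.1, says: "The cumulative probability of response by 18 weeks of age will be estimated by the Kaplan-Meier method for each vaccine arm". All three attach the 20% decision rule to that estimate in the ITT set. SAP 9.1.2 repeats the horizon with a link back to the responder definition: "The cumulative probability of anti-rotavirus serum IgA response (as defined above) by 18 weeks of age will be estimated by the Kaplan-Meier method". That section covers primary and secondary endpoints in both the PP and ITT sets. It then adds Newcombe-Wilson and GEE analyses, both tied to dose 3.

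The week 18 blood is labelled "Post IP Dose 4 Visit 9 (Week 18)" in SAP 20.1.16.

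**The concern.** A decision rule and the endpoint it is meant to test point to different samples. Under the responder definition, the last neonatal blood that counts is the Visit 7 sample. Under the literal horizon, the Visit 9 sample counts too. Two programmers could code different Kaplan-Meier results, and both could cite the SAP.

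The choice is not neutral. No RV3-BB is given to the neonatal arms between Visits 7 and 9, and Protocol 3.6.1 describes high wild-type exposure in Malawian infants in the first 5 months of life. A rise first seen at Visit 9 cannot be told apart from natural infection. The arm with more non-responders at week 14 has more infants left to convert. Counting Visit 9 would therefore narrow a real titre difference and favour non-inferiority.

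**Working it through.** **Which sample is which (neonatal arms, nominal weeks).** Doses 1 to 3 are given at birth, week 6 and week 10; placebo dose 4 is given at week 14.

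- Endpoint sample: 10 + 4 = week 14, the Visit 7 pre-dose blood (Protocol 6.9).
- Literal 18-week horizon: also the Visit 9 blood, 18 - 10 = 8 weeks after the last RV3-BB dose and 4 weeks after placebo.

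**The four statements of the horizon.**

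| Place | Horizon | Link to the doses 1-3 definition |
|---|---|---|
| Protocol synopsis | 18 weeks of age | None |
| Protocol 13.1 | 18 weeks of age | None |
| SAP 7.1.4 | 18 weeks of age | None |
| SAP 9.1.2 | 18 weeks of age | Yes, refers back to the definition |

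**Number per arm.** The plan gives 172 per arm. With 50% response in both arms, a 20-point margin, one-sided 0.025 and 90% power: n = (1.960 + 1.282)² × (0.25 + 0.25) / 0.20² = 131.4, so 132. Then 132 × 1.3 = 171.6, so 172, which reproduces the stated figure. With 30% excluded, 172 × 0.7 = 120 per arm are expected in the PP set. The point does not depend on this calculation; it only supplies n = 120.

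**Dilution.** Let pH and pL be the true week-14 response in the high-titre and lower-titre arms, and w the share of non-responders who convert in weeks 14-18, equal in both arms. Counting Visit 9:

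- each rate p becomes p + w(1 - p);
- the difference becomes (pH - pL)(1 - w).

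Take a true difference at the margin, 50% v 30%. The documents give no value of w, so these are assumptions. The error rate is the exact binomial probability that the upper limit of the 95% Newcombe interval without continuity correction falls below 20 points. It stands in for the Kaplan-Meier interval, whose variance method the SAP does not specify.

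| Assumed w | Rates counting Visit 9 | Difference (points) | False non-inferiority, 120 per arm | 172 per arm |
|---|---|---|---|---|
| 0 | 50.0% v 30.0% | 20.0 | 2.7% | 2.8% |
| 5% | 52.5% v 33.5% | 19.0 | 3.9% | 4.0% |
| 10% | 55.0% v 37.0% | 18.0 | 5.6% | 5.7% |
| 15% | 57.5% v 40.5% | 17.0 | 7.7% | 8.2% |

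A plain normal approximation at 120 per arm gives 2.5%, 3.6%, 5.0% and 6.8%, the same pattern.

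**Does the direction need equal w?** Not exactly. The difference shrinks whenever wL(1 - pL) exceeds wH(1 - pH). At 50% v 30% that means wH below (0.7/0.5) × wL = 1.4 wL.

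**Infant arm.** Its third RV3-BB dose is at week 14, so 14 + 4 = week 18 is the nominal endpoint visit. Protocol 6.11 sets "Visit 9 (Week 18 ±7 days)", that is, days 119 to 133; 18 weeks is day 126.

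**The case against.** The strongest reply is that the plan, read as a whole, already excludes Visit 9. SAP 9.1.2 applies Kaplan-Meier to the response defined just above it, and that definition stops at dose 3 in the neonatal arms. The endpoint lists stop at the same point, and SAP 9.1.5 confines neonatal vaccine take to doses 1-3. On this view 18 weeks is simply the end of follow-up (Protocol 5.1), applied to an event that can no longer occur after Visit 7. This is a fair reading of SAP 9.1.2. It therefore does not follow that the sponsor plans to count post-placebo samples. What remains is that the other three places state the decision rule without that link, so the documents leave the choice open.

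Second, the exposure is limited. Newcombe-Wilson and GEE are fixed after dose 3, and the ITT analyses are called supportive (SAP 6.1.3). Both points stand. But SAP 9.1.2 puts Kaplan-Meier and the 20% rule first and applies them to the PP set as well.

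Third, w is assumed. A reader might take it from the 40.4% placebo seropositivity in Protocol 3.6.1. At a constant hazard that gives 10.9% over 4 weeks if reached by 18 weeks, or 9.1% if reached by 5 months. The protocol does not give the age at that measurement, the figure comes from another trial, and seropositivity is not a 3-fold rise. It makes 10% plausible but does not establish it. Nor can every rise at Visit 9 be called natural infection: the documents do not exclude a late vaccine response.

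Finally, a reader might infer that 18 weeks is wrong for the infant arm too, because a strict cut at day 126 would lose 7 of the 15 days in the Visit 9 window. The documents do not support this. Week 18 is that arm's correct nominal horizon, and the SAP nowhere says that Kaplan-Meier time is actual age cut at day 126. SAP 7.1.1 uses nominal visits without windowing, although it says so only for by-visit summaries. The infant arm is also outside the titre comparison.

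**Conclusion.** The point holds for the Kaplan-Meier rule in the neonatal arms. Its literal horizon conflicts with the objective, the endpoint and the responder definition, and only one of its four statements points to the reading that removes the conflict.

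On the literal reading, a true difference at the margin shrinks to 20(1-w) points. For assumed w of 5% to 15%, false non-inferiority rises from 2.7% to between about 4% and 8% at 120 per arm. The size rests on w, on similar conversion across arms, on 50% v 30%, and on the Newcombe interval as a stand-in; the direction needs only roughly similar conversion. If the true response rates are equal, no difference is created or hidden. The dose-3 analyses are unaffected, and the infant arm needs only a clarification of the time scale.

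**What to change.** In the Protocol synopsis, Protocol 13.1, SAP 7.1.4 and SAP 9.1.2, replace the 18-weeks-of-age horizon with: by the sample after the third RV3-BB dose (Visit 7 in the neonatal arms, Visit 9 in the infant arm), by nominal visit. State that neonatal Visit 9 IgA does not count towards response; it can still be used in the titre summaries and to describe conversion after week 14.

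For the infant arm, the nominal-visit wording only ensures that Visit 9 samples taken after day 126 but within the window are kept.

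The cost is one phrase in four places and one added sentence. It needs no new data and no change to the sample size.
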